[Part 2 of 2 of the document. The other parts are not shown.]

1. All participants must be screened with HBV serologic markers: HBsAg, HBsAb, and HBcAb.
2. If HBsAg and/or HBcAb are positive, test for HBV-DNA.
3. Refer to [Table 6-10](#) for actions to be taken based on screening HBV results.
4. If a participant is HBsAg positive or HBV-DNA positive BUT is not on antiviral therapy:
  - a. Consult a physician with expertise in managing HBV
  - b. Initiate antiviral therapy with entecavir 0.5 mg q.d. 1-2 weeks prior to first dose of study treatment (capmatinib + nazartinib). Note: ongoing participants prior to initiation of Amendment 3 follow the Urgent Safety Measure.
  - c. If a participant cannot take entecavir or if entecavir is not available at your institution, contact Novartis to select an appropriate antiviral therapy.
  - d. If antiviral therapy cannot be given, the participant is not eligible for study treatment (capmatinib + nazartinib).
  - e. During the study, monitor HBV-DNA every 4 weeks (or more frequently if clinically indicated). (Refer to [Table 6-11](#) if there is evidence of viral reactivation on study)
  - f. Antiviral therapy should continue for at least 4 weeks after the last dose of study treatment (capmatinib + nazartinib).
5. Participants who are HBsAg positive or HBV-DNA positive at screening and already have been receiving antiviral therapy are eligible provided the participant remains on antiviral treatment.
  - a. Identify a consulting physician with expertise in managing HBV who can provide treatment guidance, if required, while the participant is on study.
  - b. HBV-DNA should be monitored every 4 weeks (or more frequently if clinically indicated).
  - c. Antiviral therapy should continue for at least 4 weeks after the last dose of study treatment (capmatinib + nazartinib).
6. Refer to [Table 6-11](#) for guidelines of management for HBV reactivation.

**Table 6-10 Actions to be taken based on hepatitis B results screening**

Test	Result	Result	Result	Result	Result
HBV-DNA	+	+ or -	-	-	-
HBsAg	+ or -	+	-	-	-
HBsAb	+ or -	+ or -	+ and no prior HBV vaccination	- or + with prior HBV vaccination	- or + with prior HBV vaccination
HBcAb	+ or -	+ or -	+ or -	+	-
Required actions	
* Consult a physician with expertise in managing HBV. After the consultation, antiviral therapy should be started 1-2 weeks prior to first dose of study treatment (capmatinib + nazartinib). Recommended antiviral therapy is entecavir 0.5 mg q.d. Contact Novartis if a participant cannot take entecavir or if entecavir is not available at your institution. Monitor HBV-DNA every 4 weeks (or more frequently if clinically indicated). Antiviral therapy should continue for at least 4 weeks after the last dose of study treatment (capmatinib + nazartinib).
		
No antiviral therapy. Monitor HBV-DNA every 4 weeks.
		
No antiviral therapy. HBV-DNA screening not required unless if HBsAg and/or HBcAb are positive

*Recommended antiviral therapy is entecavir 0.5 mg q.d. Contact Novartis if a participant cannot take entecavir or if entecavir is not available at your institution. Antiviral therapy should continue for at least 4 weeks after the last dose of study treatment (capmatinib + nazartinib).
					

**Table 6-11 Guidelines for management of HBV reactivation**

HBV reactivation (with or without clinical signs and symptoms)*		
Screening test results	Monitoring test results that define HBV reactivation	Actions to be taken
Positive HBV-DNA OR Positive HBsAg	Increase of 1 log in HBV-DNA relative to screening HBV-DNA value OR new appearance of measurable HBV-DNA	
Interrupt study treatment (capmatinib + nazartinib). Assess participant compliance with antiviral therapy. Consult a physician with expertise in managing HBV and consider changing antiviral therapy.
 
While participant is on antiviral therapy, continue interruption of study treatment (capmatinib + nazartinib) administration until resolution to:
 
 
• ≤ screening HBV-DNA levels and
 
• ≤ grade 1 ALT (or baseline ALT, if > grade 1) if ALT elevation was observed
 
 
If resolution occurs within ≤ 21 days study treatment (capmatinib + nazartinib) should be re-started at the same dose level unless dose reduction/interruption is indicated due to any other reason. Antiviral therapy should continue for at least 4 weeks after the last dose of study treatment (capmatinib + nazartinib).
 
If resolution occurs > 21 days Contact Novartis for approval of restarting of study treatment (capmatinib + nazartinib).
 
 
• If restarting of study treatment (capmatinib + nazartinib) is approved: follow the same guidelines as above.
 

HBV reactivation (with or without clinical signs and symptoms)*		
Screening test results	Monitoring test results that define HBV reactivation	Actions to be taken
		
 
If restarting of study treatment (capmatinib + nazartinib) is NOT approved: discontinue study treatment (capmatinib + nazartinib). Continue antiviral therapy for at least 4 weeks after the last dose of study treatment (capmatinib + nazartinib).
 
 
Monitor HBV-DNA every 4 weeks (or more frequently if clinically indicated).

### **HCV screening tests, on study monitoring, and management of HCV reactivation**

1. Screen all new participants for HCV Ab. If HCV Ab is detected then check HCV-RNA.
2. Only participants with negative HCV Ab or with positive HCV Ab but undetectable level of HCV-RNA are eligible to be dosed with study treatment (capmatinib + nazartinib) (assuming all other eligibility criteria are met). Participants with detectable HCV-RNA are not eligible to be enrolled in the study.
3. The following two categories of participants should be monitored every 8 weeks (or more frequently if clinically indicated) with HCV RNA-PCR for HCV reactivation:
  - a. Participants with detectable HCV-RNA at screening and were treated until HCV-RNA becomes undetectable (only applicable to participants enrolled prior to Amendment 3)
  - b. Participants with known history of HCV infection and undetectable HCV-RNA at screening
4. Refer to [Table 6-12](#) for definition of HCV reactivation and the management guidelines.

**Table 6-12 Guidelines for management of HCV reactivation**

HCV reactivation (with or without clinical signs and symptoms) 		
Screening test results	Monitoring test results that define HCV reactivation	Action to be taken
Knowledge of past hepatitis C infection with no detectable HCV-RNA OR Detectable HCV-RNA at screening and was treated until HCV-RNA becomes undetectable 	New appearance of detectable HCV-RNA	
Interrupt study treatment (capmatinib + nazartinib). Consult a physician with expertise in managing HCV. After the consultation, start antiviral therapy.
 
While participant on antiviral therapy, continue interruption of study treatment (capmatinib + nazartinib) administration until resolution to:
 
 
no detectable HCV-RNA and
 
≤ grade 1 ALT (or baseline ALT, if > grade 1) if ALT elevation was observed.
 
 
If resolution occurs within ≤ 21 days study treatment (capmatinib + nazartinib) should be re-started at the same dose level unless dose reduction/interruption is indicated due to any other reason.
 
If resolution occurs > 21 days Contact Novartis for approval of restarting of study treatment (capmatinib + nazartinib).
 
 
If restarting of study treatment (capmatinib + nazartinib) is approved: follow the same guidelines as above.
 
If restarting of study treatment (capmatinib + nazartinib) is NOT approved: permanently discontinue the participant from study treatment (capmatinib + nazartinib).
 
 
Monitor HCV-RNA every 4 weeks (or more frequently if clinically indicated)

 All reactivations of HCV are to be recorded as serious adverse event (SAE). Date of viral reactivation is the date on which the defined lab results for reactivation were met (e.g., for a participant whose HCV-RNA was detectable on 01-JAN-15 and ALT reached > 5 x ULN on 22-JAN-15, the date of viral reactivation is 22-JAN-15).
 
 Applicable to ongoing participants only
		

**On study monitoring of liver function test (LFT) for all participants**

LFTs should be monitored for all participants as per protocol, or more frequently if clinically indicated.

At any time during the study, if ALT > 5 x ULN in participants with baseline ALT ≤ 3 x ULN, or if ALT > 8 x ULN in participants with baseline ALT > 3 x ULN but ≤ 5 x ULN: **immediately**

1. Perform test(s) for viral hepatitis infection or reactivation: all participants should be screened with viral hepatitis panel (HA Ab-IgM, HBsAg, HBcAb-IgM, and HC Ab). In addition
  - a. Participants who have HBV-DNA monitoring during the study should be re-tested for HBV-DNA immediately; refer to [Table 6-11](#) for definition and management of HBV reactivation.
  - b. Participants who have HCV-RNA monitoring during the study should be re-tested for HCV-RNA immediately; refer to [Table 6-12](#) for definition and management of HCV reactivation.
2. If any of the above tests indicate:

- a. HBV reactivation: refer to [Table 6-11](#) for management guidelines.
  - b. HCV reactivation: refer to [Table 6-12](#) for management guidelines.
  - c. New viral infection: immediately interrupt study treatment (capmatinib + nazartinib), consult a physician with expertise in managing viral hepatitis and contact Novartis for further discussion.
3. Perform other relevant tests/procedures as clinically indicated.
  4. Follow the dosing modification for ALT elevation according to guidelines in [Table 6-7](#).

### 6.3.3 Guidelines for the management and dose modification of skin-related toxicities

Rash, particularly maculopapular rash or rash pruritic, is an adverse event frequently observed following treatment with nazartinib. Participants must be closely monitored for any signs/symptoms related to rash/skin toxicities. Recommended guidelines for management and dose modification of rash/skin toxicities are provided in [Table 6-13](#), [Table 6-14](#), and [Table 6-15](#).

Recommended dose modifications apply to both nazartinib and capmatinib.

**Table 6-13 Guidelines for prevention and symptomatic care of rash/skin toxicities**

Type of care	Action
Prevention/Prophylaxis Starting from Day 1 for all participants	
 
• Avoid unnecessary exposure to sunlight/ultraviolet
 
• Apply broad-spectrum sunscreen with SPF<math>\geq</math>15 at least twice daily
 
• Use thick, alcohol-free emollient cream (e.g. glycerine and cetomacrogol cream) on dry areas of the body at least twice daily
 

Symptomatic care*	
 
• Pruritic lesions: cool compresses and oral antihistamine therapies
 
• Desquamation: thick, alcohol-free emollient cream and mild soap
 
• Paronychia: antiseptic bath and topical antibiotics; if no improvement, consult dermatologist
 
• Infected lesions: appropriate topical or systemic antibiotics
 

*Participants who develop rash/skin toxicities should be evaluated by a qualified physician and receive symptomatic and supportive care management.	

**Table 6-14 Management and dose modification for maculopapular rash**

Initial CTCAE Grade	Adverse Event Management	Action and Dose Modification
Grade 1	
 
• Initiate appropriate symptomatic care (Refer to Table 6-13)
 
• Use mild-strength topical steroid (e.g. 1% hydrocortisone cream) on affected areas
 
• Re-assess every week
 
	Continue nazartinib and capmatinib at same dose level
Grade 2	
 
• Initiate appropriate symptomatic care (Refer to Table 6-13)
 
• Use moderate-strength topical steroid (e.g. 2.5% hydrocortisone cream or 0.5% fluticasone cream) on affected areas PLUS low-dose oral steroid (e.g. 5 mg-10 mg PO q.d. for 1 week) with taper
 
	Continue nazartinib and capmatinib at same dose level 
 
• If no recovery or worsened within 1 week, interrupt nazartinib and capmatinib until recover to <math>\leq</math> Grade 1. Once rash has recovered to <math>\leq</math> Grade 1, restart nazartinib and capmatinib at one
 

Initial CTCAE Grade	Adverse Event Management	Action and Dose Modification
	
 
Re-assess every week
 
	
level reduced from the previous dose level

Grade ≥3	
 
Initiate appropriate symptomatic care (Refer to Table 6-13)
 
Use moderate-strength topical steroid on affected areas PLUS mid-dose oral steroid (e.g. 20-40 mg PO q.d. for 1 week) with taper over 1-2 weeks or i.v. steroid (e.g. methylprednisolone 20-30 mg i.v. b.i.d. for 3 days) if clinically indicated
 
Consult dermatologist
 
Reassess every week
 
	
 
Interrupt nazartinib and capmatinib until rash recovers to ≤ Grade 1. Once recovers to ≤ Grade 1, restart study drug at one level reduced from the previous dose level.
 
Oral antihistamine therapies (e.g. levocetirizine 5 mg q.d., desloratadine 5 mg q.d., or fexofenadine 180 mg q.d.) should be given concurrently with study drug for 4 weeks when restarting treatment.
 
If no recovery to ≤ Grade 2 within 3 weeks, permanently discontinue study drug
 
Participants who develop more than 1 episode of Grade ≥ 3 rash will be permanently discontinued from study drug
 


 Maculopapular rash includes macular rash, papular rash, and maculopapular rash.   For all grades of maculopapular rash, consider skin biopsy for pathologic evaluation. Study drugs may be resumed although steroids are still ongoing or being tapered.   A maximum of 2 dose reductions is allowed. Participants, who require further dose decrease after 2 dose reductions, should be discontinued from study drug. Escalation by one level to previous dose level may be considered if no rash is evident after 4 weeks of uninterrupted study drug at the reduced dose level. Re-escalation can only be done once.
		

**Table 6-15 Management and dose modification for other rashes including acneiform rash**

Initial CTCAE Grade	Adverse Event Management	Action and Dose Modification
Grade 1	
 
Monitor for change in severity and consider symptomatic and/or topical treatment (Refer to Table 6-13)
 
Re-assess every 2 week
 
	Continue study drug at same dose level
Grade 2	
 
Initiate appropriate symptomatic care (Refer to Table 6-13)
 
Depending on the type of rash, a variety of agents can be used including mild to moderate strength steroid creams, topical or systemic antibiotics, topical or systemic antihistamines, and retinoid creams.
 
Re-assess every 2 week
 
	Continue study drug at same dose level 
 
If no recovery or worsened within 2 weeks, interrupt study drug until rash recovers to ≤ Grade 1
 
Once rash recovers to ≤ Grade 1, then restart study drug at one reduced dose level*
 

Grade ≥3	
 
Initiate appropriate symptomatic care (Refer to Table 6-13)
 
Depending on the type of rash, a variety of agents can be used including mild to moderate strength steroid creams, low-dose oral steroids, etopical or systemic antibiotics, topical or systemic antihistamines, and retinoid creams.
 
Consult dermatologist
 
Reassess every 2 week
 
	Interrupt study drug until rash recovers to ≤ Grade 1. -Once rash recovers to ≤ Grade 1, restart study drug at one reduced dose level* 
 
If no recovery to ≤ Grade 2 within 3 weeks, permanently discontinue study drug
 
Participants who develop more than 1 episode of Grade ≥3 rash will be permanently discontinued from study treatment
 

\*A maximum of 2 dose reductions is allowed. Participants, who require further dose decrease after 2 dose reductions, should be discontinued from study drug. Escalation **by one level** to previous dose level may be considered if no rash is evident after 4 weeks of uninterrupted study drug at the reduced dose. Re-escalation can only be done once.

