### 6.3.4 Follow-up for toxicities

Participants whose treatment is interrupted or permanently discontinued due to an adverse event or clinically significant laboratory value, must be followed up at least once a week (or more frequently if required by institutional practices, or if clinically indicated) for 4 weeks, and subsequently at approximately 4-week intervals, until resolution or stabilization of the event, whichever comes first. Appropriate clinical experts should be consulted as deemed necessary. All participants must be followed up for adverse events and serious adverse events for 30 days following the last doses of nazartinib and capmatinib.

An unscheduled assessment should be performed in all cases below where toxicity monitoring is recommended more frequently than defined by the schedule of assessments. Subsequent monitoring must be performed as per the regular visit schedule.

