≥ CTCAE grade 3	Intensify appropriate skin toxicity therapy and monitor weekly or more frequently until resolved to grade ≤ 1
Peripheral edema	
CTCAE grade ≤ 2	Consider to initiate conservative measures such as leg elevation, compression stockings, and dietary salt modification as clinically indicated
CTCAE grade ≥ 3	Initiate/intensify conservative measures
RESPIRATORY, THORACIC AND MEDIASTINAL DISORDERS	
ILD/Pneumonitis	
CTCAE Grade 1	
CT scan (high-resolution with lung windows) recommended, with serial imaging to monitor for resolution or progression- re-image at least every 3 weeks
 
Monitor for symptoms every 2-3 days - Clinical evaluation and laboratory work-up for infection

TOXICITY	FOLLOW-UP EVALUATION
	Monitoring of oxygenation via pulse oximetry recommended Consultation of pulmonologist recommended
CTCAE Grade 2	CT scan (high-resolution with lung windows) 
 
• Monitor symptoms daily, consider hospitalization
 
• Clinical evaluation and laboratory work up for infection
 
• Consult pulmonologist
 
• Pulmonary function tests a - if normal at baseline, repeat every 8 weeks
 
• Bronchoscopy with biopsy and/or Bronchoalveolar Lavage (BAL) recommended c
 
 Symptomatic therapy including corticosteroids if clinically indicated (1 to 2 mg/kg/day prednisone or equivalent as clinically indicated) b
CTCAE Grade 3 and Grade 4	CT scan (high-resolution with lung windows) Clinical evaluation and laboratory work-up for infection Consult pulmonologist Pulmonary function tests a - if < normal, repeat every 8 weeks until ≥ normal Bronchoscopy with biopsy and/or BAL if possible c Treat with i.v. steroids (methylprednisolone 125 mg) as indicated. When symptoms improve to ≤ Grade 1, a high dose oral steroid (prednisone 1 to 2 mg/kg once per day or dexamethasone 4 mg every 4 hr) b If i.v. steroids followed by high dose oral steroids does not reduce initial symptoms within 48 to 72 hours, consider non-corticosteroid immunosuppressive medication

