### 7.1.4 Discontinuation from study treatment and from study

Participants may voluntarily discontinue from the study treatment for any reason at any time. If a participant decides to discontinue from the study treatment, the investigator should make a reasonable effort (e.g. telephone, e-mail, letter) to understand the primary reason for this decision and record this information in the participant's chart and on the appropriate CRF pages. They may be considered withdrawn/opposition to use data/biological samples, if they state an intention to withdraw/opposition to use data/biological samples, fail to return for visits, or become lost to follow-up for any other reason.

The investigator must discontinue study treatment for a given participant if he/she believes that continuation would be detrimental to the participant's well-being.

Discontinuation from study treatment is required under the following circumstances:

- Adverse events and laboratory abnormalities meeting criteria for study treatment discontinuation: refer to [Section 6.3](#).
- Pregnancy
- Interruption of one of the study drugs for 21 consecutive days or more, regardless of reason for study drug interruption
- Use of prohibited treatment, refer to [Appendix 4](#).
- Any other protocol deviation that results in a significant risk to the participant's safety.

Participants who discontinue from study treatment agree to return for the end of treatment and follow-up visits indicated in the Assessment Schedule (refer [Section 7](#)). In addition, before a new anti-neoplastic therapy is initiated for a participant, it is strongly recommended to perform a tumor assessment. If they fail to return for these assessments for unknown reasons, every effort (e.g. telephone, email, letter) should be made to contact them as specified in [Section 7.1.7](#).

For Phase II, the investigator must also contact the IRT to register the participant's discontinuation from study treatment.

Discontinuation from study is when the participant permanently stops receiving the study treatment, and further protocol-required assessments or follow-up, for any reason.

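### The Grade ≥3 row of Table 6-15 prints a two-weekly rash reassessment, where Section 6.3.4 and Table 6-16 call for weekly follow-up

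*Protocol*

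**What the plan says.** **Table 6-15 (other rashes, including acneiform).** The Grade 1 and Grade 2 rows print "Re-assess every 2 week". The Grade ≥3 row gives the same interval, spelled without the hyphen. At Grade ≥3 drug is interrupted at once and restarted one dose level lower when the rash has recovered to Grade 1 or better. The row also carries a stop rule: "If no recovery to ≤ Grade 2 within 3 weeks, permanently discontinue study drug".

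**Section 6.3.4.** Participants whose treatment is interrupted or stopped for an adverse event "must be followed up at least once a week" for 4 weeks, and about every 4 weeks after that until resolution or stabilization. The section adds: "An unscheduled assessment should be performed in all cases below where toxicity monitoring is recommended more frequently than defined by the schedule of assessments".

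**Table 6-16, Rash and Photosensitivity, Grade 3 or higher.** "Intensify appropriate skin toxicity therapy and monitor weekly or more frequently until resolved to grade ≤ 1". No rash type is excepted.

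**Table 6-14 (maculopapular rash), Grade ≥3.** Same interruption and same 3-week stop rule, with weekly reassessment.

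**Section 6.3.3.** This introduces the three rash tables: "Recommended guidelines for management and dose modification of rash/skin toxicities are provided in" Tables 6-13 to 6-15.

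**Section 7.1.4.** Discontinuation from study treatment is required after "Interruption of one of the study drugs for 21 consecutive days or more, regardless of reason for study drug interruption".

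**The concern.** Everyone in the Grade ≥3 row of Table 6-15 is interrupted for an adverse event, so everyone in it falls under the weekly rule of Section 6.3.4. Yet the cell that a site would consult for this particular rash gives an interval twice as long. A site following that cell alone breaches a mandatory requirement without noticing.

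What is at stake is treatment continuity. Restart depends on recovery to Grade 1 or better, and Section 7.1.4 ends treatment at 21 consecutive days of interruption. Seeing the participant less often makes late detection of recovery more likely, and with it a longer hold or, near the limit, a lost chance to restart.

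**Working it through.** No sample size, power or error rate is involved. The check sets the texts side by side and then compares two visit grids.

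**Step 1: what each text asks for once Grade ≥3 rash has led to interruption**

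| Place | Interval | Force |
|---|---|---|
| Table 6-15, Grade ≥3 | every 2 weeks | recommended (Section 6.3.3) |
| Section 6.3.4 | at least weekly for 4 weeks | must |
| Table 6-16, rash, Grade 3 or higher | weekly or more often, to Grade 1 or better | follow-up table under Section 6.3.4 |
| Table 6-14, Grade ≥3 | weekly | recommended (Section 6.3.3) |

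Only the Table 6-15 cell differs. The two-week interval makes sense in the Grade 2 row of that table: drug continues there, and the row's decision point is also 2 weeks. At Grade ≥3 drug is held and the row's own deadline is 3 weeks, so that reason does not carry over.

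**Step 2: number of looks in the first 4 weeks**

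- Table 6-15 alone: 28 / 14 = 2 looks (days 14 and 28).
- Section 6.3.4: 28 / 7 = 4 looks as a minimum (days 7, 14, 21 and 28).

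**Step 3: when recovery is first seen, if only these looks are used**

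| Recovery on days | Two-weekly look | Weekly look | Difference |
|---|---|---|---|
| 1–7 | 14 | 7 | 7 days |
| 8–14 | 14 | 14 | 0 days |
| 15–21 | 28 | 21 | 7 days |
| 22–28 | 28 | 28 | 0 days |

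Measured from recovery itself, the longest wait is 14 − 1 = 13 days on the two-weekly grid and 7 − 1 = 6 days on the weekly one.

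**Step 4: the 21-day limit**

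If dosing restarts at look L, the missed days are L − 1 when day 0 is the last dose taken, and L when day 0 is the first dose withheld.

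- Day 14: 13 or 14 missed days, within the limit.
- Day 21: 20 or 21 missed days, so the result turns on the counting convention.
- Day 28: 27 or 28 missed days, over the limit on either count.

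A recovery in the third week that went unnoticed until day 28 would therefore be past the limit.

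**Step 5: where the ordinary visit schedule leaves room for this**

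Table 7-1 has Days 1, 8, 15 and 22 in Cycles 1 and 2 for Phase Ib and Groups 1 to 4, so a weekly look exists there anyway. Later cycles have Days 1 and 15, with the Day 15 hematology and chemistry ending at Cycle 6. The Group 5 schedule lists only Day 1 of each 28-day cycle, in monotherapy and in the combination extension. The exposed periods are thus mainly Cycle 3 onward and Group 5.

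**The case against.** The strongest reply is that the protocol already deals with this. Section 6.3.4 is mandatory, Table 6-16 repeats it for rash, and Table 6-15 is only recommended. Weekly visits satisfy all of them, so a site that reads the whole of Section 6.3 has no gap. That stands and limits the point to a contradiction in an operational table. It does not remove the point: the pages shown state no order of precedence, and the rash-specific cell is the one most likely to be used by itself.

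Three stronger readings are tempting, and the document does not support them.

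- **A reader might infer that every participant recovering on days 15 to 20 would lose treatment.** That assumes no other contact. Restart is triggered by recovery, not by a scheduled look. The row requires a dermatologist consultation, the footnote to Table 6-13 requires evaluation by a physician, and Section 8.1.1 requires ongoing events to be assessed at each visit. Loss of treatment is possible, not certain.
- **A reader might infer that the missing day-21 look defeats the 3-week stop rule.** This is largely moot. Under Section 7.1.4 anyone held for 21 days or more is discontinued whatever the rash grade, so the exact grade on day 21 seldom changes the decision.
- **A reader might infer a safety hazard from continued dosing.** Drug is held throughout, so there is none.

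The day-21 result in step 4 also shows that a weekly look does not by itself settle the 21-day limit. That is a question of how Section 7.1.4 counts days, and it is separate from the two-weekly cell.

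**Conclusion.** The contradiction is printed and real. The Grade ≥3 interval in Table 6-15 conflicts with the mandatory weekly follow-up in Section 6.3.4 and with Table 6-16, and it differs from the parallel row of Table 6-14.

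Its effect is bounded. With Section 6.3.4 followed, it is nil. With Table 6-15 followed alone, there are 2 looks instead of at least 4 in 28 days, and recovery may be detected 7 days later than on a weekly grid. The possible harm is a delayed restart or, through the 21-day limit, an avoidable loss of treatment.

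This rests on the following:

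- The looks fall exactly on the grid days, with no other contact in between.
- The text at hand gives no rate of Grade ≥3 rash of this type, so no number of participants can be stated.
- The first part of the protocol is not shown, so a precedence rule there cannot be excluded.
- Section 6.3.3 describes rash as a nazartinib effect. In Group 5 the clearer case is therefore the combination extension.

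It is a minor point, worth correcting because the correction is so cheap.

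**What to change.** In the Grade ≥3 row of Table 6-15, change the reassessment interval from every 2 weeks to every week, in line with Section 6.3.4, Table 6-16 and the Grade ≥3 row of Table 6-14. Leave the Grade 1 and Grade 2 rows as they are. No extra rule on the day of the third visit is needed for this point.

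The cost is one table cell in an amendment. No contacts are added beyond those that Section 6.3.4 already requires.
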